9.7.1.6.3 EXPLORATORY EFFICACY ANALYSES

(revised per Amendments 01 and 02)

An MMRM will be used to analyze the following exploratory endpoints:

- Change from baseline in the derived ADCOMS at 12 months in MCI/Prodromal and mild to moderate AD subjects
- Change from baseline in total hippocampal atrophy at 12 and 18 months in mild to moderate AD subjects as measured by vMRI
- Change from baseline in CSF A β (1-x) and CSF A β (1-42) after 4 weeks and 18 months in MCI/Prodromal and mild to moderate AD subjects. Data from early discontinuations will also be included.
- Change from baseline in the clinical assessments: ADAS-cog, CDR, MMSE, ISLT, CBB, and FAQ at 12 weeks and at 6, 9, 12, 15, 18, 19, and 21 months in MCI/Prodromal and mild to moderate AD subjects
- Change from baseline in plasma and CSF amyloid and CSF BACE1 measurements after 4 weeks and 18 months of treatment, and during posttreatment follow-up in MCI/Prodromal and mild to moderate AD subjects
- Change from baseline in left and right hippocampal, whole brain, and total ventricular volume at 6, 12 and 18 months as measured by vMRI in MCI/Prodromal and mild to moderate AD subjects

A linear mixed-model will be used to analyze the following exploratory endpoints:

- Change from baseline in brain amyloid levels as measured by amyloid PET at 18 months in MCI/Prodromal and mild to moderate AD subjects
- Change from baseline in CSF biomarkers of neurodegeneration (eg, tau, p-tau) at 18 months of treatment in MCI/Prodromal and mild to moderate AD subjects

Data from early discontinuations will also be used as appropriate. Comparisons between each treatment group and placebo will be performed.

A linear mixed-model with repeated measures will be used to determine the relationship between the following endpoints:

- Change from baseline in the derived ADCOMS score and the change from baseline in biomarkers in CSF at 18 months in MCI/Prodromal and mild to moderate AD subjects
- Change from baseline in the derived ADCOMS score and change from baseline in imaging biomarkers (hippocampal, whole brain, and total ventricular volumes) at 12 and 18 months in MCI/Prodromal and mild to moderate AD subjects

ApoE status for heterozygous and homozygous E4 carriers will be included in the model to assess the effect of *ApoE* status in this relationship.

9.7.1.7 Pharmacokinetic, Pharmacodynamic, Pharmacogenomic, and Other Biomarker Analyses

9.7.1.7.1 PHARMACOKINETIC ANALYSES

The Safety Analysis Set will be used for individual E2609 concentration listings. The PK Analysis Set will be used for summaries of E2609 concentrations.

9.7.1.7.2 PHARMACODYNAMIC, PHARMACOGENOMIC, AND OTHER BIOMARKER ANALYSES

Pharmacodynamic, PGx, and other biomarker analyses may be performed and reported separately. Details of these analyses may be described in a separate statistical analysis plan. Please also refer to [Appendix 3](#).

Pharmacodynamic Analyses

The PD Analysis Set will be used for the summaries and analyses of PD biomarkers (CSF and plasma biomarkers, MRI endpoints). CSF A β (1-x), A β (1-42), t-tau, p-tau, and BACE1 will be assessed and data will be presented graphically. Baseline levels and changes in t-tau and p-tau will be correlated with changes in CSF A β (1-42), imaging markers, and *ApoE4* status.

Summary statistics for CSF biomarkers will be assessed for evidence of a dose relationship.

Pharmacokinetic and Pharmacodynamic Analyses

The PK/PD relationship between CSF biomarker levels and exposure to E2609 in CSF will be explored graphically and any emergent relationship will be explored through population PK/PD modeling. The PK/PD relationship between plasma PK parameters with other biomarkers may also be explored using similar methods.

Additionally, the relationship between plasma and CSF exposure to E2609 and the derived ADCOMS at 18 months, and the relationship between plasma and CSF exposure to E2609 and the change from baseline for 18 months in the ADAS-cog, the CDR, and the MMSE, will be explored graphically. Any emergent relationship will be explored through population PK/PD modeling.

Exposure-safety analyses may also be conducted.

Pharmacogenomic Analyses

Blood samples will be used to determine the *ApoE* genotype and the *NAT2* phenotype of subjects enrolled in this study. The genomic DNA samples may also be stored and used as

described in [Section 9.7.1.7.2](#). Details of PGx testing may be provided and reported separately.

9.7.1.8 Safety Analyses

Evaluations of safety will be performed on the Safety Analysis Set. The incidence of AEs (including changes from baseline in physical and neurological examinations, and dermatological assessments), out-of-normal-range laboratory safety test variables, abnormal ECG findings, out-of-range vital signs, suicidality (C-SSRS), and results of the sleep questionnaire, along with the change from baseline in laboratory safety test variables, ECGs, safety MRI, and vital sign measurements will be summarized by treatment group using descriptive statistics.

9.7.1.8.1 EXTENT OF EXPOSURE

The extent of exposure to study drug will be summarized as cumulative extent of exposure in 3-month intervals. The number and percent of subjects will be presented by treatment group. Duration of exposure will be summarized using descriptive statistics in 3-month intervals. The number and percent of subjects will be presented by treatment group.

9.7.1.8.2 ADVERSE EVENTS

The AE verbatim descriptions (investigator terms from the eCRF) will be classified into standardized medical terminology using the Medical Dictionary for Regulatory Activities (MedDRA). Adverse events will be coded to the MedDRA (Version 17.0 or higher) lower level term closest to the verbatim term. The linked MedDRA preferred term and primary system organ class (SOC) are also captured in the database.

A TEAE is defined as an AE that emerges during treatment, having been absent at pretreatment (Baseline) or

- Reemerges during treatment, having been present at pretreatment (Baseline) but stopped before treatment, or
- Worsens in severity during treatment relative to the pretreatment state, when the AE is continuous.

Only those AEs that are treatment-emergent will be included in summary tables. All AEs, treatment-emergent or otherwise, will be presented in subject data listings.

The TEAEs will be summarized by treatment group on the Safety Analysis Set. The incidence of TEAEs will be reported as the number (percentage) of subjects with TEAEs by SOC and preferred term. A subject will be counted only once within an SOC and preferred term, even if the subject experienced more than 1 TEAE within a specific SOC and preferred term. The number (percentage) of subjects with TEAEs will also be summarized by maximum severity (mild, moderate, or severe). The number (percentage) of subjects with

TEAEs will also be summarized by relationship to study drug (Yes [related] and No [not related]).

The number (percentage) of subjects with treatment-related TEAEs will be summarized by SOC and preferred term. Treatment-related TEAEs include those events considered by the investigator to be related to study drug. The number (percentage) of subjects with treatment-related TEAEs will also be summarized by maximum severity (mild, moderate, or severe).

Adverse events will be summarized by the following subgroups: *ApoE4* status (positive or negative), prior treatment with AChEIs or memantine (no or yes), and clinical population (MCI/Prodromal or mild to moderate AD). (revised per Amendment 01)

The number (percentage) of subjects with TEAEs leading to death will be summarized by MedDRA SOC and preferred term for each treatment group. A subject data listing of all AEs leading to death will be provided.

The number (percentage) of subjects with treatment-emergent SAEs will be summarized by MedDRA SOC and preferred term for each treatment group. A subject data listing of all SAEs will be provided.

The number (percentage) of subjects with TEAEs leading to discontinuation from study drug will be summarized by MedDRA SOC and preferred term for each treatment group. A subject data listing of all AEs leading to discontinuation from study drug will be provided.

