9.5.1.5.1 ADVERSE EVENTS AND EVENTS ASSOCIATED WITH SPECIAL SITUATIONS

An AE is any untoward medical occurrence in a subject or clinical investigation subject administered an investigational product. An AE does not necessarily have a causal relationship with the medicinal product. For this study, the study drug is E2609.

The criteria for identifying AEs in this study are:

- Any unfavorable and unintended sign (including an abnormal laboratory finding), symptom, or disease temporally associated with the use of an investigational product, whether or not considered related to the investigational product (Note: It is not necessary to report every sign or symptom as a separate AE if the overall disease [diagnosis] is being reported as an AE.)
- Any new disease or exacerbation of an existing disease
- Any deterioration in nonprotocol-required measurements of a laboratory value or other clinical test (eg, ECG or x-ray) that results in symptoms, a change in treatment, or discontinuation of study drug
- Recurrence of an intermittent medical condition (eg, headache) not present pretreatment (Baseline)

- An abnormal laboratory test result should be considered an AE if the identified laboratory abnormality leads to any type of intervention, discontinuation of study drug, or withholding of study drug, whether prescribed in the protocol or not

All AEs observed during the study will be reported on the eCRF. All AEs, regardless of relationship to study drug or procedure, should be collected beginning from the time the subject signs the study ICF through the last visit (Visit 20, as shown in [Table 7](#)). For subjects who discontinue early from study drug but undertake further efficacy assessments, AEs will only be collected for 3 months after the last dose of study drug, ie, through to the second follow-up visit (Visit 20). Subjects who fail screening primarily due to AE(s) must have the AE(s) leading to screen failure reported on the Screening Disposition eCRF. SAEs will be collected for 3 months after the last dose of study drug, ie, through to the second follow-up visit (Visit 20). For subjects who discontinue early from study drug but continue with further efficacy assessments, SAEs will be solicited only for 3 months after the last dose of study drug, i.e. up to the 2nd follow up visit (Visit 20). However, any SAEs volunteered by subjects after this time point must be reported according to standard procedures.

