9.7.1.8.3 LABORATORY VALUES

Laboratory results will be summarized using International System of Units, as appropriate. For all quantitative parameters listed in [Section 9.5.1.5.3](#), the actual value and the change from baseline to each postbaseline visit and to the end of treatment (defined as the last on-treatment value) will be summarized by visit and treatment group using descriptive statistics. Qualitative parameters listed in [Section 9.5.1.5.3](#) will be summarized using frequencies (number and percentage of subjects), and changes from baseline to each postbaseline visit and to end of treatment will be reported using shift tables. Percentages will be based on the number of subjects with both nonmissing baseline and relevant postbaseline results.

Laboratory test results will be assigned a low/normal/high (LNH) classification according to whether the value was below (L), within (N), or above (H) the laboratory parameter's reference range. Within-treatment comparisons for each laboratory parameter will be based on 3-by-3 tables (shift tables) that compare the baseline LNH classification to the LNH classification at each postbaseline visit and at the end of treatment. Similar shift tables will also compare the baseline LNH classification to the LNH classification for the highest and lowest value during the treatment period.

Appendix 1 (Sponsor's Grading for Laboratory Values) presents the criteria that will be used to identify subjects with treatment-emergent markedly abnormal laboratory values (TEMAVs). Except for phosphate, a TEMAV is defined as a postbaseline value with an increase from baseline to a Grade of 2 or higher. For phosphate, a TEMAV was defined as a postbaseline value with an increase from baseline to a Grade of 3 or higher. When displaying the incidence of TEMAVs, each subject may be counted once in the laboratory parameter high and in the laboratory parameter low categories, as applicable.

Lymphocyte subsets (ie, CD4 [T helper cells], CD8 [cytotoxic T cells], CD19 [B cells], CD16/CD56 [natural killer cells] and CD14 [macrophages]) and regulatory T cells will be summarized in the same manner as other laboratory parameters. Mean lymphocyte subsets and the mean change from baseline in lymphocyte subsets will also be displayed graphically over time by dose.

Serum IgG, IgM, and IgA will be measured and summarized in the same manner as other laboratory parameters.

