| Calcium, serum-low (hypocalcemia) (conversion to mmol×0.25) | <8.5 – 8.0 mg/dL <2.13 – 2.0 mmol/L | <8.0 – 7.0 mg/dL <2.0 – 1.75 mmol/L | <7.0 – 6.0 mg/dL <1.75 – 1.5 mmol/L | <6.0 mg/dL <1.5 mmol/L |
| Calcium, serum-high (hypercalcemia) | >10.6 – 11.5 mg/dL >2.65 – 2.9 mmol/L | >11.5 – 12.5 mg/dL >2.9 – 3.1 mmol/L | >12.5 – 13.5 mg/dL >3.1 – 3.4 mmol/L | >13.5 mg/dL >3.4 mmol/L |
| Cholesterol, serum-high (hypercholesterolemia) (conversion to mmol/L ×0.02586) | 0 -19 years >169 – 300 mg/dL >4.37 – 7.75 mmol/L 19 -150 years >199 – 300 mg/dL >5.15 – 7.75 mmol/L | >300 – 400 mg/dL >7.75 – 10.34 mmol/L | >400 – 500 mg/dL >10.34 – 12.92 mmol/L | >500 mg/dL >12.92 mmol/L |
| Creatinine | Female >1.00 mg/dL – 1.5×1.00 Male >1.27 mg/dL – 1.5×1.27 | Female >1.5 – 3.0×1.00 Male >1.5 mg/dL – 3.0×1.27 | Female >3.0 – 6.0×1.00 Male >3.0 mg/dL – 6.0 ×1.27 | Female >6.0×1.00 Male >6.0×1.27 |
| Gamma glutamyl transpeptidase | Female >60 IU/L – 3.0×60 Male >65 IU/L – 3.0×65 | Female >3.0 – 5.0×60 Male >3.0 – 5.0×65 | Female >5.0 – 20.0×60 Male >5.0 – 20.0×65 | Female >20.0×60 Male >20.0×65 |
| Glucose, serum-high (hyperglycemia) (conversion to mmol/L ×0.0555) | Fasting glucose value >99 – 160 mg/dL >5.5 – 8.9 mmol/L | Fasting glucose value >160 – 250 mg/dL >8.9 – 13.9 mmol/L | >250 – 500 mg/dL; >13.9 – 27.8 mmol/L; hospitalization indicated | >500 mg/dL; >27.8 mmol/L; life-threatening consequences |
| Glucose, serum-low (hypoglycemia) | <65 – 55 mg/dL <3.6 – 3.0 mmol/L | <55 – 40 mg/dL <3.0 – 2.2 mmol/L | <40 – 30 mg/dL <2.2 – 1.7 mmol/L | <30 mg/dL <1.7 mmol/L life-threatening consequences; seizures |
| Phosphate, serum-low (hypophosphatemia) (conversion to mmol/L ×0.323) | not applicable | <2.5 – 2.0 mg/dL <0.8 – 0.6 mmol/L | <2.0 – 1.0 mg/dL <0.6 – 0.3 mmol/L | <1.0 mg/dL <0.3 mmol/L life-threatening consequences |
| Potassium, serum-high (hyperkalemia) | not applicable | >5.5 – 6.0 mmol/L | >6.0 – 7.0 mmol/L hospitalization indicated | >7.0 mmol/L life-threatening consequences |
| Potassium, serum-low (hypokalemia) | <3.5 mEq/L – 3.0 mmol/L | <LLN – 3.0 mmol/L; symptomatic; intervention indicated | <3.0 – 2.5 mmol/L hospitalization indicated | <2.5 mmol/L life-threatening consequences |
| Sodium, serum-high (hypernatremia) | >144 mEq/L – 150 mmol/L | >150 – 155 mmol/L | >155 – 160 mmol/L hospitalization indicated | >160 mmol/L life-threatening consequences |

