reductions in CD4 (T helper cells), CD8 (cytotoxic T cells), and CD19 (B cells) counts at Day 8. These reductions were more clearly evident by Day 15, consistent with a treatment by time interaction in the statistical analysis. There was evidence that the lower doses of 50 to 100 mg also caused some reduction in CD4 lymphocyte counts by Day 15. Doses above 100 mg appeared to be associated with greater reductions in CD4 and CD8 lymphocyte counts, which occurred earlier in the treatment period compared with the effects of 25 to 100 mg doses. These effects on lymphocyte counts gradually resolved from Day 20 to Day 35, which were 6 and 21 days, respectively, after administration of the last dose of E2609 on Day 14. Reductions in CD4 and CD8 lymphocyte counts at doses of 200 and 400 mg to a level close to or less than the lower limit of normal (LLN) could be associated with increased risk of developing relapse of orolabial herpes or other infections.

In Study 003, a drug-drug interaction study, PK results showed that itraconazole (a potent inhibitor of cytochrome P450 [CYP3A4] and carboxyesterase-2 [CES2]) increased by approximately 70% the area under the concentration \times time curve (AUC) of E2609. Consequently, strong inhibitors of CYP3A4 will be prohibited in this study.

Rifampin (a potent CYP3A4 inducer) caused a mild decrease (by approximately 20%) of the AUC of E2609. Therefore, no restrictions are required for the use of concomitant medications which are known to be inducers of CYP450 enzymes. Donepezil (a moderate CES2 inhibitor) caused a mild increase (by approximately 20%) of the AUC of E2609 when coadministered with E2609 but not when dosed at least 2 hours apart from E2609. E2609 (which inhibits the P-glycoprotein 1 transporter) did not affect the PK properties of digoxin. Nonclinical studies also indicated that other CYP pathways apart from CYP3A4 would not be major pathways of metabolism of E2609. Therefore, on the basis of drug interaction considerations, the only restriction of concomitant medications is that for strong inhibitors of CYP3A4.

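### New-onset adverse events in the 12-week follow-up are collected but kept out of the by-arm AE tables, and three Appendix 1 rows leave TEMAV status indeterminate

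*Protocol*

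**What the plan says.** **Adverse events.** Section 9.7.1.8.2 opens its definition with: "A TEAE is defined as an AE that emerges during treatment, having been absent at pretreatment (Baseline) or". It adds two further routes, re-emergence and worsening in severity, and ties both to the treatment period as well. The rule for output follows: "Only those AEs that are treatment-emergent will be included in summary tables". The tables of deaths, SAEs and discontinuations in the same section are likewise confined to treatment-emergent events. Other events go to listings: "All AEs, treatment-emergent or otherwise, will be presented in subject data listings".

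Collection runs longer. Section 9.5.1.5.1 gathers AEs from consent to Visit 20. For subjects who stop drug early but keep attending efficacy visits it says: "AEs will only be collected for 3 months after the last dose of study drug". Section 9.1.2 treats the 78-week Treatment Period and the 12-week Follow-Up Period as separate.

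**Laboratory values.** In Section 9.7.1.8.3, for every analyte except phosphate, "a TEMAV is defined as a postbaseline value with an increase from baseline to a Grade of 2 or higher". The grades come from Appendix 1, where the male creatinine Grade 2 entry begins "Male >1.5 mg/dL".

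**The concern.** Safety, including immunological and hematological parameters, is a primary objective (Section 8.1). For the multiple-dose study, Section 7.1 reports that the effects on lymphocyte counts "gradually resolved from Day 20 to Day 35, which were 6 and 21 days, respectively, after administration of the last dose". It adds that CD4 and CD8 counts falling close to or below the lower limit of normal could raise the risk of herpes relapse or other infection. Section 9.3.3 stops study drug for confirmed low counts and for certain infections and rashes. It follows subjects stopped with an infection for 12 weeks or longer. The protocol therefore expects that relevant events may occur off drug, yet its table rule gives a new-onset event in that period no place in a by-arm comparison. Listings do not give incidence by dose.

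In Appendix 1, a value that satisfies two grades on opposite sides of the TEMAV threshold can be counted or not, at the programmer's choice.

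**Working it through.** **1. AE window.** Inputs: Sections 9.1.2, 9.5.1.5.1, 9.7.1.5, 9.7.1.8.2 and 9.7.1.8.3.

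- Collection: consent to 12 weeks after the last dose.
- Tabulation: onset, return or worsening during treatment. No lag is stated. Where the protocol needs an end of treatment elsewhere, it uses the last dose: concomitant medication runs to that date (9.7.1.5), and end of treatment for laboratory data is the last on-treatment value (9.7.1.8.3).
- Difference: events that begin or worsen between the last dose and Visit 20 are collected and listed, but not tabulated.

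Share of post-first-dose collection time outside the tables:

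- completer: 12 / (78 + 12) = 13.3%
- illustrative subject stopped at Week 4: 12 / (4 + 12) = 75%

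These are shares of calendar time, not of events. The Week 4 stopper is an example, not a figure from the protocol.

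Timing of the known effect, with the last dose on Day 14: Day 20 − 14 = 6 days and Day 35 − 14 = 21 days. Both fall inside the 84-day follow-up.

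**2. Appendix 1.** Each graded row was turned into numeric intervals (one sex or age band where bands share a structure), and every pair of grades was tested for overlap. Three rows overlap:

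| Row | Grades | Printed limits | Overlap |
|---|---|---|---|
| Uric acid | 1 and 3 | same text in both; Grade 2 not applicable | women >7.1 to 10, men >8.6 to 10 mg/dL |
| Creatinine, men (literal) | 1 and 2 | Grade 1 ends at 1.5 × 1.27 = 1.905; Grade 2 starts at 1.5 mg/dL | 1.5 to 1.905 mg/dL |
| Creatinine, men (literal) | 2 and 3 | Grade 2 ends at 3.0 × 1.27 = 3.81; Grade 3 starts at 3.0 mg/dL | 3.0 to 3.81 mg/dL |
| Potassium, low | 1 and 2 | both from the lower limit (3.5, taken from Grade 1) to 3.0 | 3.0 to 3.5 mmol/L |

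Examples: a man's uric acid of 9 mg/dL is Grade 1 (not a TEMAV) and Grade 3 (a TEMAV if baseline was lower). A man's creatinine of 1.7 mg/dL is Grade 1 and, literally, Grade 2. A potassium of 3.2 mmol/L is Grade 1 or 2 depending on symptoms or intervention, which a laboratory value does not carry. The creatinine 2/3 overlap matters less, because both grades are already at or above the Grade 2 threshold. It can change TEMAV status only for a subject who was Grade 2 at baseline.

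If the male creatinine lower limits are read as multiples of 1.27, the overlap disappears. No other row checked overlaps, including white cells, lymphocytes and neutrophils.

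**The case against.** **The analysis plan may set the window.** Section 9.7.1 leaves further detail to the SAP, which is not shown, and on-treatment windows are often set there. That would answer a protocol that was silent. This one states both a definition and a rule that only events meeting it are tabulated, so a lag in the SAP would change the text rather than complete it. The point stands, on the reading that treatment ends with the last dose.

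**Little is lost.** A reader might infer that follow-up data vanish from all safety summaries. They do not. Section 9.7.1.8.3 summarizes laboratory values, lymphocyte subsets and immunoglobulins at each postbaseline visit, and a TEMAV may be any postbaseline value. Follow-up events remain in the listings, and the DSMB reviews all safety data unblinded (Section 9.1). An event that causes discontinuation begins on treatment, so it is already treatment-emergent; so is one that begins on treatment and continues afterwards. All of this stands, and it confines the gap to new-onset or newly worsened AEs, SAEs and deaths after the last dose.

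**The lymphocyte data do not call for 84 days.** They cover 6 to 21 days, and the clearest reductions were at 200 and 400 mg, although Section 7.1 also reports some CD4 reduction at 50 to 100 mg and the top dose here is 50 mg. This stands: the data support having some window, not a particular length.

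**Creatinine is shorthand.** ALT, AST, GGT and bilirubin also print lower limits without the multiplier, so the male row may simply carry a stray unit. That is plausible, but those rows print no unit there and the male creatinine row does. Women are unaffected because their upper limit is 1.00.

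**Conclusion.** The point holds in a limited form.

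1. Section 9.7.1.8.2, followed as written, leaves AEs, SAEs and deaths with onset in the 12 weeks after the last dose out of the by-arm AE tables. This assumes that treatment ends at the last dose, as the protocol uses the term elsewhere.
2. TEMAV status is indeterminate for parts of three Appendix 1 rows: uric acid (a plain duplication), low potassium (not separable on laboratory values alone) and male creatinine (on the literal mg/dL reading).

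A reader might go further and infer that dose-related risk is understated, or that TEMAVs are over-counted or wrong in general. The documents support neither. They give no post-dose event rates, so neither the size nor the direction of any effect by arm can be computed. Values in the overlaps also meet the lower grade, so the counts are ambiguous, not shown to be too high. The 13.3% describes collection time only.

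The change is worth making because safety is a primary objective and the data are already being collected.

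**What to change.** **Section 9.7.1.8.2.** Either state a post-dose window for treatment-emergence, with its length justified, or keep the on-treatment tables and add by-arm tables of AEs, SAEs and deaths with onset between the last dose and Visit 20. The second option avoids choosing a window and keeps the on-treatment incidence undiluted. The cost is some programming and some background events in the new tables.

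**Appendix 1.** Make the three rows mutually exclusive:

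- Male creatinine: write the lower limits of Grades 2 and 3 as >1.5×1.27 and >3.0×1.27, so that they meet the upper limits of the grades before them.
- Uric acid: reconcile the Grade 1 and Grade 3 entries.
- Low potassium: reconcile the Grade 1 and Grade 2 entries so that a laboratory value alone decides the grade, or state how symptoms and intervention will be captured for TEMAV assignment.

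The cost is appendix wording. No new data are needed unless symptoms or intervention are kept as a potassium criterion.
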